The primary objective is to assess the efficacy of fractionated carbon dioxide laser in improving surgical scars. Objective assessment of the scars will involve the Vectra microtopographic imaging system to measure changes in the length of the scar. The Patient and Observer Scar Assessment Scale (POSAS) is a validated survey that will be utilized for subjective assessments of the vascularity, pigmentation, thickness, pliability, surface area, relief, pain, and pruritus.

The secondary objective will be to evaluate the tolerability of the laser, by assessing the severity and duration of known side effects of laser therapy such as erythema, edema, burning sensation, post-inflammatory pigment changes, infection, scarring, xerosis, pruritus, bronzing, and any other adverse events that arise following treatment. Patients will be given a 30-diary after each treatment to document this information.

Selection and Withdrawal of Study Subjects

Study Population

The study population will consist of 50 adult patients 18 years of age or older with surgical scars located on the head and neck.

Minors are not included due to the Mohs patient population being adults only who have undergone surgical excisions of skin cancers on the head or neck. Although participants are not

required to be patients in the Mohs clinic, scars and healing may be significantly different in children, making the data less reliable and difficult to interpret.

Inclusion and Exclusion Criteria

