A screening visit will occur whereby patients deemed appropriate for the study will have the segment of the scar with the most deformity defined for objective evaluation at each session. Baseline photographs of this area will be obtained and demographic data about the surgery that created the scar, associated wound healing complications, age of the scar, and the Fitzpatrick skin phototype will be collected. Randomization will occur at this visit and patients will receive their first treatment at this visit. Prior to treatment application, subjects will cleanse their face with a gentle cleanser, such as Cetaphil, provided in the office in order to remove all lotion, creams, make up, and sunscreen. An optional topical or local anesthetic medication will be offered to the subject and if desired by the subject will be applied to the treatment area approximately 20 minutes prior to the procedure. If the scar is deeper, an injection of numbing medicine (lidocaine with epinephrine) may be used as well. Once this time passes and the numbing medicine is working, the subject will be escorted to the procedure room. The treatment areas will be wiped clean of the numbing cream prior to the procedure. Just prior to the procedure, the subject's eyes will be covered with eye shields to protect their eyes. The treatment time may vary, but generally takes 10 minutes or less. During this time, subjects will hear the laser, which sounds like a bee buzzing, and will feel some warmth. Most patients report minimal discomfort during the procedure. There may be pinpoint bleeding, bruising, and crusting depending upon the area and extent of the treatment. After the treatment, patients will be provided with a 30-day diary to daily record treatment-related reactions: redness, swelling, pain, itching or color changes following treatment. If the subject has a history of recurrent fever blisters/cold sores on the lips or face, the subject will be offered a three day prescription for an antiviral medication that the subject can fill at the subject's pharmacy to prevent a recurrence since laser treatments may increase the chance of recurrent episodes. The subject would take one pill every twelve hours the day prior to treatment, on the treatment day, and the first day post-treatment. The subject or their insurance plan must cover the cost of the medication. This may delay the treatment to a later date within 30 days of the screening visit. If antibiotic/antiviral medications are needed, you and/or your insurance company will be responsible for covering this cost.

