 - Expect the treated area to be red for several weeks. You can use makeup starting three days after the treatment, but it is best to wait until the skin has fully exfoliated and becomes pink to red shiny, smooth skin. This usually takes 7 to 10 days.
 - Some swelling may develop, and generally lasts 1-2 days. It is recommended that you sleep in a slightly elevated position to help relieve swelling.
 - It is common to feel a heat or sunburn sensation in the treated areas. This heat will dissipate over the next few hours. Cold compresses, such as ice, may help soothe the heat and can be gently applied to the skin.
 - Pain is uncommon after the first few days, and usually subsides with Tylenol and cooling the skin. Itching can be seen, and will usually last a few days or less. You can press on the clean itchy skin with a cotton tipped applicator (i.e. Q-tip) to relieve the itching. Avoid scratching the skin.
 - Normal daily activities may be resumed immediately after treatment. Avoid strenuous exercise, bending, straining, stooping or lifting heavy objects for 48 hours. These activities may cause swelling and pain in the treatment area. If a patient is not able to receive the treatment on the same day as the screening and randomization visit (possibly due to an ongoing oral herpetic infection), they may return to the office within 30 days for their first treatment.

Study Visit #2

The subject will be asked to return in 3 months for a second treatment visit with the following activities:

- The subject will complete a pre-treatment questionnaire
- o The subject will receive laser treatment as randomized to high energy or low energy treatment
- The subject will obtain post-treatment instructions
- The subject will obtain a paper diary to record possible reactions such as redness, swelling, pain, itching or color changes following treatment
- If the subject has a history of recurrent fever blisters/cold sores on the lips or face, the subject will be offered a three day prescription for an antiviral medication that the subject can fill at the subject's pharmacy to prevent a recurrence since laser treatments may increase the chance of recurrent episodes. The subject would take one pill every twelve hours the day prior to

treatment, on the treatment day, and the first day post-treatment. The subject or their insurance plan must cover the cost of the medication. This may delay the treatment to a later date within 30 days of the screening visit.

Study Visit #3

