The safety of subjects will be maintained. Subjects will be provided with information about the risks associated with laser therapy, severity, and time course for resolution will be addressed during the consent process. Such risks include the following: infection (days, mild, reversed with topical antivirals), pinpoint bleeding (occasionally occurs, resolves with application of pressure dressing), scarring (uncommon, varies, may be ameliorated with different laser settings), erythema (very common, severity varies, resolves over a few days to months with sun avoidance and sunscreen use), postinflammatory hyperpigmentation (occasionally occurs, varies, reverses with sunscreen use), and delayed-onset hypopigmentation (occasionally occurs, varies, self-resolves with sunscreen use), bronzing (common, varies, reverses with daily sunscreen use and time), exposure to laser smoke, visible skin patterns, damaged skin, distortion of anatomic features, acute pain, crusting (very common, severity varies, resolves over days), pruritus (common, varies, ameliorated with neutralizing moisturizer and self-resolves), edema (common, varies, self-resolves days to weeks) xerosis (commonly occurs, mild-to-moderate, reverses with neutralizing moisturizer cream), allergic reactions, delayed healing, surgical anesthesia, additional treatment or surgery may be necessary.

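### The 30-day diary named for the duration-of-side-effects objective stops short of the plan's own range for redness; after day 30 the end date rests on the coarser general adverse-event process

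*Combined protocol and SAP*

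**What the plan says.** Under Study Objectives/Primary and Secondary: "The secondary objective will be to evaluate the tolerability of the laser, by assessing the severity and duration of known side effects". Erythema heads the list of effects, and the same paragraph names the record: "Patients will be given a 30-diary after each treatment to document this information". Study Procedures gives the length and frequency: "patients will be provided with a 30-day diary to daily record treatment-related reactions".

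The plan describes the expected course of redness in two places. The post-treatment instructions under Study Visit #1 tell subjects: "Expect the treated area to be red for several weeks". The Safety section lists "erythema (very common, severity varies, resolves over a few days to months with sun avoidance and sunscreen use". Safety also lists "delayed-onset hypopigmentation (occasionally occurs, varies, self-resolves with sunscreen use", with no onset time. Other reactions are expected to be short; for example, "Some swelling may develop, and generally lasts 1-2 days".

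The next scheduled contact comes well after the diary ends. Under Study Visit #2: "The subject will be asked to return in 3 months for a second treatment visit". Unscheduled Visits gives a two-week window either side of the three months.

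Reporting of Adverse Events provides a second route. Onset, duration and severity are recorded for each AE. Subjects are told to report AEs and are asked about them at each visit in open-ended terms, with specific questions about events already reported. AEs are followed until they are normal or clinically acceptable in the PI's judgement. Data Protection describes the PI as the only unblinded person in the study. Data Analysis and Statistical Considerations gives no analysis of diary data and no rule for a reaction still present when the diary ends.

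**The concern.** Duration is half of the secondary objective, and the instrument assigned to it cannot observe the upper part of the range the plan itself gives for its most prominent reaction. Once the diary ends, measurement passes from a blinded subject's daily entry to a process with three weak points:

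- A subject told that redness is normal has little reason to report it. The plan does not say whether expected redness is to be logged as an AE.
- The routine question is non-specific and comes about 3 months after treatment, so redness that faded in between would be dated by recall or missed.
- Follow-up may stop at a level the PI finds acceptable, which is not the same as resolution, and the PI knows the assignment.

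Redness still present at Visit 2 is then followed by the second treatment, and the two reactions can no longer be separated.

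How long the skin stays red is something a patient choosing between energy levels would want to know. If the high-energy arm stays red longer, that is where the comparison would be measured least well.

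**Working it through.** **Calendar (from the documents).** The plan states no figure on this point to reproduce.

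- Diary: 30 days, or 30/7 = 4.3 weeks. Redness of 3 or 4 weeks (21 or 28 days) fits; 5 weeks (35 days) does not, nor does anything measured in months.
- Next visit: about 91 days, with window 77 to 105. The diary covers 30/91 = 33% of the interval (30/105 = 29% to 30/77 = 39%).
- Gap from diary end to next visit: 91 − 30 = 61 days, with range 77 − 30 = 47 to 105 − 30 = 75.

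**Assumptions for the rest.** The plan gives no distribution of durations. I assume a lognormal duration with median m and log-scale SD s of 0.5 or 0.8, redness in every subject, and 25 per arm (50 subjects split equally). The first two calculations also assume that the AE record adds nothing after day 30.

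**1. Can an arm's median be reported if unresolved redness is correctly censored at day 30?** At least 13 of 25 must have cleared: P(Binomial(25, p) ≥ 13), with p = Φ((ln 30 − ln m)/s).

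| True median (days) | p (s = 0.5 / 0.8) | Chance reportable |
|---|---|---|
| 21 | 0.762 / 0.672 | 99.8% / 96.4% |
| 28 | 0.555 / 0.534 | 71.1% / 63.6% |
| 31.5 | 0.461 / 0.476 | 34.7% / 40.3% |
| 42 | 0.250 / 0.337 | 0.3% / 4.5% |

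With observation to day 77, the earliest next visit, the lowest value in the table would be 99.88%, given full completion of the added entries.

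**2. What if unresolved redness were entered as 30 days?** The plan does not say this would be done; it simply has no rule against it. With T_H and T_L the durations in the longer and shorter arm, the share of the true mean difference (to day 91) that is kept is [E min(T_H,30) − E min(T_L,30)] / [E min(T_H,91) − E min(T_L,91)].

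| Medians (days) | s = 0.5 | s = 0.8 |
|---|---|---|
| 5 vs 10 | 5.58/5.67 = 98% | 5.67/6.81 = 83% |
| 14 vs 21 | 5.69/7.91 = 72% | 4.37/8.63 = 51% |
| 14 vs 28 | 9.38/15.70 = 60% | 7.21/16.34 = 44% |
| 21 vs 31.5 | 4.94/11.59 = 43% | 3.88/11.20 = 35% |
| 21 vs 42 | 7.17/22.34 = 32% | 6.02/20.33 = 30% |

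**3. What if the AE process works fully?** Here all redness past day 30 is logged as an AE and its end is dated by recall with log-scale error. The true medians are 21 and 42 days, and results come from simulation (s = 0.5 / 0.8).

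| Source of end dates after day 30 | Difference in medians (days) | Standard error (days) |
|---|---|---|
| Weekly entries | 21.2 / 21.4 | 6.3 / 9.9 |
| AE record, recall error SD 0.3 | 20.5 / 20.9 | 7.1 / 10.8 |
| AE record, recall error SD 0.5 | 19.3 / 19.7 | 8.7 / 12.2 |

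Complete AE logging therefore recovers most of what the diary misses. Incomplete logging, which this calculation leaves out, puts the result somewhere between this and calculation 1.

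**The case against.** The strongest reply is that the AE section already covers long redness. Persistent redness fits the plan's AE definition, duration is a required item, events already reported are asked about specifically, and follow-up continues past day 30. Photographs, the blinded evaluation and the POSAS vascularity and pigmentation items also show the state of the scar at each assessment. A reader might infer from the diary's length that redness beyond day 30 has no prospective end date at all. The documents do not support that, because the AE provisions can supply one. Calculation 3 shows that if they are applied to every case, the extra gain from weekly entries is modest.

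Two further points stand. Several weeks may mean 3 or 4, which fits in the diary; only the Safety wording about months clearly exceeds it. The medians of 28 days and above are assumptions.

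The reply falls short on one thing: nothing in the plan makes the AE route apply to expected redness. Status at a visit does not say when redness ended, and the PI-judged end point is neither blinded nor tied to full resolution.

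A reader might also infer that the cut-off could create a false difference between arms. It would not: if durations are the same in both arms, which is possible because the energy ranges overlap, both are truncated alike.

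**Conclusion.** The concern holds in a limited form. The instrument named for duration does not span the plan's own range for redness, and the fallback is coarser, dependent on reporting, and partly unblinded. Severity and short reactions (swelling, itching, early pain) are little affected, and the percent still red at day 30 can be had from the present diary. What is weakly measured is how long redness lasts beyond day 30, and pigment change that first appears after it.

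The size is uncertain. Little is lost if redness usually clears within about 3 weeks. If it typically lasts 4 to 6 weeks, the diary alone would often fail to give a median. The figures in calculations 1 and 2 are illustrative upper bounds on the loss: they assume the durations and ignore the AE record, and calculation 2 also assumes an entry rule the plan does not contain. This is a secondary tolerability objective and the primary comparison is untouched. The change should be made because it is cheap, but the trial does not depend on it.

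**What to change.** 1. Keep the daily 30-day diary. For any reaction still present at day 30 or appearing later, add one tick-box entry per week until it has gone or the next visit.
2. Collect the diary at that visit. The Visit 2 list, which may be abbreviated, shows no diary return, so state it there.
3. Log each such reaction as an AE with a resolution date.
4. In Data Analysis and Statistical Considerations, report descriptively by randomised arm, up to Visit 3 and separately after each treatment: the percent with redness or colour change still present at day 30 and at the next visit, and the Kaplan-Meier median duration with its 95% CI. Take the end date as the midpoint between the last entry with the reaction and the first without. Censor unresolved reactions at the last entry or at re-treatment; do not enter them as 30 days.

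If the diary is not extended, the minimum is to report the percent still red at day 30 by arm and to say that longer durations are not measured by the diary.

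**Cost.** No new visits. At most about (91 − 30)/7 = 8.7, so 9 entries per treatment (7 to 11 over the window), and only for subjects with a persisting or late reaction. Under the assumed durations the mean is 0.5 to 1.2 entries at a median of 21 days and 2.9 to 3.4 at 42. Some entries will be missed, and somewhat more mild reactions will be recorded in both arms.

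Estimates stay imprecise at about 25 per arm. For example, 16/25 against 8/25 still red at day 30 is a difference of 32 points (Newcombe 95% CI 4 to 54).

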For the inclusion criteria, adult patients of all Fitzpatrick phototypes who have surgical scars of the head and neck will be screened for this study. There is no data to suggest that there is a difference in the appearance of older (more than 1 year old from the initial injury) and newer scars (at least 8 weeks after surgery) post-therapy. Most scars are fully mature at exactly 1 year from the date of the initial injury, so in the "older scar" cohort one may presume (in the absence of any confirmed findings in the medical literature) that any changes to these scars post-therapy will be an effect from the laser. The minimum age of the scar will be eight weeks from the initial surgery, as the scar has healed enough to determine if additional fine tuning may be helpful. In addition, standard practice is to allow a scar to heal for 8 weeks before laser treatment. Therefore subjects may be enrolled in the younger scar group if the scar is 8 weeks – 51 weeks from occurrence, and enrolled in the older scar group if the scar is 52 weeks or older from time of occurrence. We will aim to recruit 20 patients with old scars (10 of which will be in the high energy treatment group, and 10 of which will be in the low energy treatment group). In terms of statistical analysis, we will review whether there is a difference between the post-treatment measurements and appearance of older scars and newer scars. Patients must be able to understand the informed consent, willing to come to the office for treatments and capable of following post-treatment instructions.

In terms of exclusion criteria, patients who have had prior laser treatments to the face and neck, have a history of keloid formation, scars resulting from non-surgical etiologies (i.e. minor trauma), isotretinoin use in the last 6 months prior to study enrollment, and allergy to topical lidocaine will not be eligible for the study.

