 - A topical anesthetic medication will be applied to the treatment area approximately 20 minutes prior to the procedure. If the scar is deeper, an injection of numbing medicine may be used as well. Once this time passes and the numbing medicine is working, the subject will be escorted to the procedure room. The treatment areas will be wiped clean of the numbing cream prior to the procedure.
 - Just prior to the procedure, the subject's eyes will be covered with eye shields to protect their eyes.
 - The treatment time may vary, but generally takes 10 minutes or less. During this time, the subject will hear the laser, which sounds like a bee buzzing, and will feel some warmth. Most report minimal discomfort during the procedure. There may be pinpoint bleeding, bruising, and crusting depending upon the area and extent of the treatment. After the treatment, the subject will be provided with a diary to daily record treatment-related reactions: redness, swelling, pain, itching or color changes following treatment.
 - The subject will be given a paper diary to record possible reactions such as redness, swelling, pain, itching or color changes following treatment

- You will be given post-treatment instructions:
 - Thoroughly wash your hands prior to touching the treatment area.
 - Gently clean the treated area with a mild cleanser 3 times per day. Splash the face with tepid water and pat dry with a paper towel or a clean soft washcloth. The goal is to lightly remove the exfoliating skin and crusting that develops after the laser procedure. This is a GENTLE process with NO scrubbing. Avoid picking or scratching at the treatment site, as the skin is very friable and sensitive. Picking or scratching can lead to pigmentation changes or further scarring.
 - After each cleaning, apply a coat of Vaseline with a cotton tipped applicator (i.e. Q-tip)
 - As the skin heals, it is common to see little dots ("peppering") all over the treated skin. These will come off with the cleansing process.
 - You will continue the wound care for 7 10 days, at which time you should begin applying sunscreen instead of Vaseline.
 - You can shower the next day and wash hair, but avoid very hot water
 - On not expose the treated area to sun or wind for at least two weeks after treatment. If you go outside, use sunscreen with zinc (SPF 30+) and wear a hat. Protecting your skin and limiting sun exposure ensures the best results.

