As soon as the PI becomes aware of an AE that meets the criteria for an SAE, the SAE should be documented to the extent that information is available. A report must be submitted by the study site to the SLU IRB, within 24 hours. Forms for reporting SAEs will be provided to the study site. SAEs will be recorded from the time of informed consent, through the end of the study. If in the opinion of the Investigator, an SAE occurring outside the specified time window (i.e., following subject completion or withdrawal from the study), is deemed to be device related, then the event should be reported with 24 hours as outlined above. The Investigator should institute any clinically necessary supplementary investigation of SAE information.

Death

In the case of subject death, any post-mortem findings/reports will be requested and a report (even if a preliminary diagnosis/cause of death is available) will be submitted to the SLU IRB within 24 hours of learning about the death.

Reporting of Pregnancy

In the case of subject pregnancy, the subjects will be discontinued from the study and will be followed leading up to delivery.

Data Analysis and Statistical Considerations

At the completion of the study, the data obtained will be reviewed and analyzed with the aid of the Saint Louis University Center for Health Outcomes Research. A chi-square test along with the Wilcoxon signed rank test will be performed to assess significant difference between clinical improvement scores between study visits. There is no data to suggest that there is a difference in the appearance of older (more than 1 year old from the initial injury) and newer scars post-therapy. We will aim to recruit 20 patients with old scars (10 of which will be in the high energy treatment group, and 10 of which will be in the low energy treatment group). In terms of statistical analysis, we will review whether there is a difference between the post-treatment measurements and appearance of older scars and newer scars.

Quality Control and Quality Assurance

Quality control and assurance for this study will be performed by an internal review every 3 months to ensure that the data collected is in accordance with the goals of this study and to address any issues with data collection or performance of any study procedures.

Direct Access, Data Handling and Record Keeping

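### The presumption that any change in older scars is a laser effect is unsupported: scar maturity rules out only maturation, and the named tests compare visits with no laser-free arm

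*Combined protocol and SAP*

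**What the plan says.** All references are to the combined protocol and SAP.

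- **Inclusion and Exclusion Criteria.** Scars of 52 weeks or more form the older group. The premise is "Most scars are fully mature at exactly 1 year from the date of the initial injury". The inference is hedged, "one may presume (in the absence of any confirmed findings in the medical literature", and concludes that "any changes to these scars post-therapy will be an effect from the laser".
- **Study Procedures.** At screening, patients have "the segment of the scar with the most deformity defined for objective evaluation at each session". Then "Baseline photographs of this area will be obtained".
- **Study Visit #1, post-treatment instructions.** Treated skin is cleansed three times a day and covered with petrolatum for about 7-10 days, after which sunscreen replaces the petrolatum. Sun avoidance, zinc sunscreen and a hat are advised, with the comment "Protecting your skin and limiting sun exposure ensures the best results".
- **Opening summary and Dose Regimen.** Both randomised arms receive laser, at high or low energy. No untreated or sham arm is described, although the Introduction calls the trial placebo-controlled.
- **Data Analysis and Statistical Considerations.** A chi-square test and a "Wilcoxon signed rank test will be performed to assess significant difference between clinical improvement scores between study visits". No test between arms is named and no significance level is given. For older scars the aim is 20 patients, 10 per arm, with a review of whether older and newer scars differ after treatment.

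**The concern.** The primary objective is the efficacy of the laser. With laser in both arms and tests only between visits, the presumption is the one stated step from before-after change to a laser claim. It rests on maturity, which excludes spontaneous maturation and nothing else, and then only for most scars.

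Three other sources of change are in the plan itself:

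- **Added care.** The aftercare and sun protection are new to the subject.
- **Expectation.** Every subject knows a laser was used, and the patient POSAS belongs to the primary objective. Blinding to energy level does not remove this.
- **Selection.** A segment picked because it looks worst on one day tends to look better on a later reading.

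Restricting attention to old scars removes none of them. At stake is a published statement that the laser improved older scars, resting on change that would have occurred without a laser effect.

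**Working it through.** **Inputs from the documents:** 20 older scars, 10 per arm; 50 subjects in all; signed rank test between visits. No alpha, SD, effect size or power is stated, so there is no figure of the plan to reproduce.

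**Assumptions:** two-sided alpha 0.05, no laser effect, normal readings.

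**1. Drift from any cause.** Let d be the mean change in units of the SD of change. Simulated signed rank tests at n = 20 (3,000 trials each) are set beside a hand check from the normal approximation 1 − Φ(1.96 − d√20). The approximation runs slightly high at this sample size.

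| d | d√20 | hand check | signed rank, simulated | between arms, 10 v 10, simulated |
|---|---|---|---|---|
| 0 | 0 | – | 4.7% | 4.5% |
| 0.2 | 0.89 | 14% | 12.7% | 4.9% |
| 0.3 | 1.34 | 27% | 23.2% | 3.9% |
| 0.5 | 2.24 | 61% | 55.3% | 4.6% |

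The between-arm column is a Mann-Whitney test of change. Drift common to both arms cancels there.

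**2. The worst-segment part.** Suppose the worst of k similar segments is picked on a reading of reliability r, and the baseline score shares that reading's error with correlation c. In SDs of a segment reading, the expected spurious improvement is

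c × (1 − r) × E(maximum of k standard normals).

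The last term is 3/(2√π) = 0.846 for k = 3 and 1.163 for k = 5.

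- k = 3, r = 0.7, c = 1: 0.3 × 0.846 = 0.25 (simulated 0.26).
- k = 5, r = 0.5, c = 1: 0.5 × 1.163 = 0.58 (simulated 0.585).
- c = 0: zero for any k and r.

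Significance rates at n = 20 (1,500 trials per cell):

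| k, r | c = 0.5 | c = 1 |
|---|---|---|
| 3, 0.9 | 7% | 12% |
| 3, 0.7 | 11% | 30% |
| 3, 0.5 | 14% | 47% |
| 5, 0.9 | 8% | 18% |
| 5, 0.7 | 16% | 50% |
| 5, 0.5 | 21% | 74% |

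With c = 0 (run at k = 3, r = 0.7) the rate is 5%, the nominal level. Over all settings run, with 10, 20 and 50 scars, the between-arm test stays at about 3-6%.

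**3. What the randomised contrast can detect.** For 80% power the detectable difference is √(2/n) × (1.96 + 0.84), with n per arm.

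- Older scars, 10 per arm: 0.447 × 2.80 = 1.25 SD.
- All subjects, 25 per arm (equal split assumed): 0.283 × 2.80 = 0.79 SD.

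**The case against.** The strongest reply is that this is a hedged sentence of rationale under eligibility, not an analysis rule. The sentence itself concedes that confirmed findings are lacking, and the data analysis section repeats its neighbours without repeating it. That is right, and a reader who inferred a formal decision rule would go beyond the text. But nothing elsewhere replaces the presumption: no between-arm test is named, and the hedge concerns missing literature, not rival causes of change.

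Two further inferences also go too far. One is that POSAS is scored on the worst segment. That segment is defined for objective evaluation, and the objective measure named in the objectives is scar length, which may regress less than appearance ratings. The other is that a signed rank test on 20 pooled older scars is planned. The stated comparison for that group is with newer scars; the pooled test in the working is an illustration.

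The design may also limit shared error. A live evaluator and two photo raters score the scars, and the documents do not say who picks the segment.

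On skin care, the wound-care phase lasts about 7-10 days, sun avoidance is advised for at least two weeks, usual moisturizers and cleansers continue, and assessment comes three months later. The effect of the added care could be small, and the documents give no figure for it or for expectation. This limits the size of the problem. It does not make the presumption sound.

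**Conclusion.** The concern holds as a fault of inference. Change after therapy in scars of 52 weeks or more cannot be credited to the laser on the ground of maturity, and with laser in both arms and only between-visit tests named, nothing in the plan separates a laser effect from other drift.

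The size is conditional. Under the stated assumptions (n = 20, two-sided 5%), drift of 0.2 to 0.5 SD of change gives significance in about 13% to 55% of trials. The worst-segment contribution runs from nominal, when the baseline score shares no error with the selection, to about 74% in the most adverse case examined (k = 5, r = 0.5, error fully shared).

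A reader might take the upper figures as this trial's false-positive rate. The documents do not support that: they give no k, reliability or degree of shared error, and they do not tie the tested scores to the selected segment.

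**What to change.** 1. In Inclusion and Exclusion Criteria, delete the presumption that change in older scars is due to the laser.
2. In Data Analysis and Statistical Considerations, add wording to this effect: before-after change in older scars is reported descriptively with a confidence interval and is not attributed to the laser; an effect of laser energy in older scars is claimed only from the randomised high-minus-low difference in change from baseline to Visit 3.
3. Where practicable, have the existing photo raters score baseline and Visit 3 images in random order without visit labels. This separates the baseline score from the reading used to pick the segment and hides time order.

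**Cost.** A few sentences, plus shuffled image sets. Photo rating would have to wait until the Visit 3 images exist, whereas the opening summary has it done after each visit. The older-scar claim becomes narrower: 10 per arm detects about 1.25 SD with 80% power, so smaller energy effects would probably be missed. The contrast addresses high versus low energy. It cannot show laser versus no laser, which would need an untreated or sham comparison that this design lacks.
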